## 12. MEASUREMENT OF EFFECT

Although the clinical benefit of NT-I7 in HIV-positive and HIV-negative patients with Kaposi Sarcoma (KS) has not yet been established, the intent of offering this treatment is to provide a possible therapeutic benefit, and thus the patient will be carefully monitored for tumor response and symptom relief in addition to safety and tolerability.

### 12.1 Antitumor Effect – Kaposi sarcoma

For the purposes of this study, patients should be re-evaluated for response according to the schedule established in the study calendar ([Section 11](#)). Kaposi sarcoma will be evaluated using a modified version (consistent with NCI studies) of the AIDS Clinical Trial Group (ACTG) Oncology Committee staging and response definitions for KS (Assessment guidelines are provided in [Appendix D](#)).

It should be noted that there is some observer variability in the evaluation of the number, size, nodularity, and color of lesions, and this must be considered when measurements are interpreted.

For evaluation of less than complete responses in participants with more than 50 lesions at entry, only the previously selected 1-3 representative areas that contain at least 20 lesions will be considered. However, complete responses still require the absence of any detectable diseases over the entire body (i.e., not confined to the representative areas).

#### 12.1.1 Methods of Evaluation for Measurable Disease

##### 12.1.1.1 KS Tumor Photography

Whole body photographs will be obtained upon entry into the study and a time of change in response (i.e. determination of partial or complete response or time of progressive disease) as well as at the end of the study. At these time points, 5 lesions (hereafter called marker lesions), representative of the patient's disease and, if possible, located on separate areas of the body will be selected. These marker lesions should be lesions that have never been treated with local therapies such as radiation therapy or intralesional injections. An attempt will be made to distribute the "marker" lesions between the representative areas and the rest of the body. Detailed photographs of these lesions will be obtained with a metric ruler beside them.

##### 12.1.1.2 Documentation of Marker Lesions

The size, color and nodularity of the marker lesions will be recorded. Documentation will depend on the number of lesions.

##### 12.1.1.3 Documentation of Extent of Disease

###### 12.1.1.3.1 Subjects with 50 or more KS lesions

For subjects with 50 or more lesions at entry, between 1 and 3 representative areas will be selected at baseline and these will be used for each subsequent evaluation. Representative areas are sections of the body (e.g. the back, a leg, an arm, etc.), which contain at least 20 KS lesions.

The total number of lesions in these representative areas will be counted and a record made of whether they are flat or raised. If, in the course of treatment, a single lesion breaks up into 2 or more smaller lesions whose area does not extend beyond the boundary of the initial lesion, these lesions will still be counted as single lesions for the purpose of assessing total numbers in defining a response to therapy.

#### 12.1.1.3.2 Subjects with fewer than 50 KS lesions

For subjects with less than 50 lesions at entry, the total number of lesions will be counted, and a record made of whether they are flat or raised.

#### 12.1.1.3.3 Additional studies for visceral KS involvement

Additional studies, including but not limited to, gastrointestinal endoscopy and bronchoscopy will be performed at baseline where clinically indicated, based on clinical evaluation of the patient.

### 12.1.2 Kaposi sarcoma Response Criteria

#### 12.1.2.1 Complete Response

The absence of any detectable residual disease, including tumor associated edema, persisting for at least 4 weeks.

- For subjects with pigmented macular skin lesions persisting after apparent complete response, a biopsy of at least one representative lesion is required to document the absence of malignant cells. If a lesion has not been biopsied, the patient may be classified as having a clinical CR.
- For subjects with visceral disease, the diagnostic radiologic or endoscopic study should be repeated if not medically contraindicated and found to be negative for evidence of disease. If such procedures are medically contraindicated but the patient has no clinical evidence of visceral disease, the patient may be classified as having a clinical CR.

#### 12.1.2.2 Clinical Complete Response

The absence of any detectable residual disease, including tumor associated edema, persisting for at least 4 weeks.

- For subjects with pigmented macular skin lesions persisting after apparent complete response, if a representative lesion has not been biopsied.

- For subjects with visceral disease, the diagnostic radiologic or endoscopic study should be repeated if not medically contraindicated and found to be negative for evidence of disease. If such procedures are medically contraindicated but the patient has no clinical evidence of visceral disease, the patient may be classified as having a clinical CR.

#### 12.1.2.3 Partial Response

No progressive disease (see below and noting, that single lesions which split up into 2 or more smaller lesions during the course of treatment will still be counted as one); no new lesions occurring in previously uninvolved areas of the body; no new visceral sites of involvement or the appearance or worsening of tumor-associated edema or effusions *and*:

- A 50% or greater decrease in the number and/or size of previously existing lesions **lasting for at least 4 weeks or**
- Complete flattening of at least 50% of all previously raised lesions (i.e., 50% of all previously nodular or plaque-like lesions become macular) **lasting for at least 4 weeks or**
- A 50% decrease in radiologically measurable visceral lesions sustained without evidence of re-growth **for at least 4 weeks or**
- A 50% decrease in radiologically measurable visceral lesions sustained without evidence of re-growth **for at least 4 weeks or**
- Subjects who otherwise meet the criteria for a CR but still have residual tumor-associated edema or effusions will be classified as having a PR.

#### 12.1.2.4 Progressive Disease

For those criteria that involve measurement of lesions in the clinic, the designation of progression should be made, when feasible, only when the criteria below have been **met in two measurements spaced at least 1 week apart**. For the assignment of progressive disease for the primary outcome analysis, progression will be defined in comparison to baseline measurements.

- An increase of 25% or more over baseline in the number of lesions and/or the size (sum of the products of the largest perpendicular diameters) of the marker lesions *or*
- A change in character from macular to plaque-like or nodular of at least 25% of the lesions *or*
- New visceral sites of involvement or progression of visceral disease *or*
- The development of new or increasing tumor-associated edema or effusion that lasts at least 1 week and interferes with the patient's normal activities.

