## 6.5 Study Treatment Beyond Progression

Immunotherapeutic agents such as NT-I7 may produce antitumor effects by potentiating endogenous cancer-specific immune responses. The response patterns seen with such an approach may extend beyond the typical time course of responses seen with cytotoxic agents and can manifest as a clinical response after an initial increase in tumor burden or even the appearance of new lesions.

Patients may be treated beyond progression as measured by ACTG criteria up to 4 doses if they meet all of the following criteria:

- There is no indication for chemotherapy
- The PI suspects increases in lesion measurements may be due to pseudoprogression based on assessment of changes in tumor burden and tumor associated symptoms
- The patient is tolerating therapy without DLTs

- There is no decrement in performance status
- There is absence of symptoms and signs indicating clinically significant progression of disease
- There is absence of symptomatic rapid disease progression requiring urgent medical care

These criteria must be met to ensure that patients are not exposed to unreasonable risks by continued use of the investigation agent in spite of progression of disease.

Subjects should remain on the trial and continue to receive monitoring according to the Study Calendar ([Section 11](#)). In addition to routine monitoring, participants with KS progression will be evaluated in 4 weeks ( $\pm 1$  week) for follow-up tumor assessment and possible removal from study.

At the time of progression of disease, patients will be re-consented and adequately informed of all FDA-approved therapy and potential clinical benefit that the patient may be foregoing in order to continue receiving the investigational product.

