#### Calculate and Record Thresholds from Baseline for Partial Response and Progressive Disease

Partial Response threshold = Total product x 0.5

Progressive Disease threshold = Total Product x 1.25

Record Product thresholds on Page 1 of the Response Sheet.

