**to entry or best response**, or a total of five new lesions in anatomic sites which were previously documented as having no evidence of cutaneous disease. For example, if a participant had a total of 40 lesions at entry on the back and the right leg and had a total of 50 lesions at follow-up on the back and the right leg that would be classified as PD. Also, if a participant had no lesions at entry on the right arm and had five lesions on the right arm at follow-up that would be classified as PD. Similarly, if a participant had 40 lesions at entry and 20 lesions at weeks **9 and 15 (a confirmed PR)** but at a subsequent visit was found to have 30 lesions (a greater than 25% increase over the best response), the participant would have PD. **PD after a confirmed CR is defined by the presence of any KS following that confirmed CR.**

Please note that "best response" may improve after the initial **confirmed PR** is documented. For example, if the **entry** number of lesions was 30 and the number of lesions decreased to 15 at weeks **9 and 15**, this would be the **initial confirmed PR**. If, at the week 18 evaluation the number of lesions decreased further, e.g., to 10, then **10 is the new "best response"** and subsequent assessments of PD for lesion counts would be with respect to the number 10, not to 15. **Furthermore, if the number of lesions at week 24 increased from 10 to 15, this increase would constitute PD, despite the fact that 15 is 50% smaller than the entry lesion count.**

**Note: If a confirmed PR has been achieved and subsequent evaluations do not meet criteria for PD or CR, this would continue to be evaluated as PR. In the example above, if the entry lesion count was 30 and the number of lesions decreased to 15 at weeks 9 and 15, then 15 is the "best response" to date. If, at week 24, the number of lesions increased to 18, this would continue to be reported as a PR because 18 is less than a 25% increase from 15. Similarly, if at week 24, the number of lesions decreased by an additional 20% to 12, this would also continue to be reported as a PR.**

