**Partial Response**

**PR** requires at least one of the highlighted criteria in the table below AND all of the categories shown on the same row, when compared to entry.

**Note:** If any of the criteria for PD have been met, even in the presence of a criterion for **PR**, it is considered PD.

**Note:** **PR** is always a comparison to entry even if there has been a prior **PR**.

Criteria for Classifying PR					
Total body or representative areas					
PR Category	Marker lesion area	Number of lesions	Number of raised lesions	Visceral or Oral KS*	Edema
1	Decrease <math>\geq 50\%</math>	<25% Increase	<25% Increase	<25% Increase of measurable lesions without unequivocal worsening of non-measurable disease	No significant increase or new sites
2	<25% Increase	Decrease <math>\geq 50\%</math>	<25% Increase	<25% Increase of measurable lesions without unequivocal worsening of non-measurable disease	No significant increase or new sites

Criteria for Classifying PR					
Total body or representative areas					
PR Category	Marker lesion area	Number of lesions	Number of raised lesions	Visceral or Oral KS*	Edema
3	<25% Increase	<25% Increase	Decrease $\geq 50\%$	<25% Increase of measurable lesions without unequivocal worsening of non-measurable disease	No significant increase or new sites
4	<25% Increase	<25% Increase	<25% Increase	Decrease $\geq 50\%$ of measurable lesions without unequivocal worsening of non-measurable disease or complete disappearance of non-measurable disease	No significant increase or new sites

\*Please note that there is no need to physically measure the visceral or oral KS.

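### Section 12.1.2.4 makes a repeat measurement the default before clinic-measured progression is called, Appendix D calls it at one visit, and Section 9.4.2 does not say which rule or which date governs PFS and DOR

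*Combined protocol and SAP*

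**What the plan says.** Section 12.1.2.4 makes a repeat the default for anything measured in the clinic: where it can be done, progression is to be called only once its criteria are "met in two measurements spaced at least 1 week apart". The threshold that follows is "An increase of 25% or more over baseline in the number of lesions and/or the size" of the marker lesions. Section 12.1 warns that "there is some observer variability in the evaluation of the number, size, nodularity, and color of lesions".

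Appendix D uses the same 25% step ("Progressive Disease threshold = Total Product x 1.25") but attaches no repeat to it for marker area, lesion count or raised-lesion count. Its examples assign progression at one follow-up visit. In section 2.2, a participant with a confirmed PR at 20 lesions who at a later visit "was found to have 30 lesions (a greater than 25% increase over the best response), the participant would have PD". The table in section 2.4 adds no repeat for these three criteria. The appendix does write confirmation out elsewhere: 4 weeks for PR and CR, and two consecutive evaluations for edema. Its PR rules add: "If any of the criteria for PD have been met, even in the presence of a criterion for" PR, the visit is scored as PD.

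Appendix D section 2 sends the reader to protocol Section 12.3 for the detailed definitions. There is no Section 12.3; the criteria are in 12.1.2. Section 9.4.2 defines PFS and duration of response by disease progression, without naming a rule or a date. Section 6.5 and Study Calendar note o say that "participants with KS progression will be evaluated in 4 weeks", give or take a week, for follow-up tumor assessment and possible removal from study.

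**The concern.** A site following Section 12 will normally wait for a second measurement. A site following the appendix, which Section 12.1 names as the assessment guidelines, will record progression at the first reading. Both can cite the protocol. The choice decides whether a PFS event exists, when a response ends, and whether a visit can count towards PR. Even where a repeat is taken, no text says whether a confirmed progression carries the date of the first or the second reading.

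The two rules also react differently to measurement error. With three separate 25% criteria tested at five visits, a one-reading rule gives chance many opportunities to cross the threshold in a participant whose disease has not changed. In a trial of up to 20 participants, a few such events visibly move a Kaplan-Meier curve.

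**Working it through.** **1. Side by side.**

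| Criterion | Section 12.1.2.4 | Appendix D 2.1-2.4 |
|---|---|---|
| Marker area | two measurements, at least 1 week apart, when feasible | one visit (4000 to 5000 mm², ratio 1.25) |
| Lesion count | same | one visit (35 to 44, ratio 1.257; 20 to 30 after PR, ratio 1.5) |
| Raised lesions | same, but worded as a change in character of 25% of lesions | one visit (20 to 25, ratio 1.25) |
| Edema | must last at least 1 week | two consecutive evaluations |

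The appendix's arithmetic is correct. The difference lies in the repeat.

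**2. No plan figure to reproduce.** The documents give no PFS event count, power, measurement error or false-progression rate. The rest is illustrative and rests on assumed errors.

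**3. Inputs.** From the documents: the 25% threshold; the five-lesion minimum in Appendix D 2.2; response visits at weeks 9, 13, 18, 27 and 36; up to 20 participants. Assumed: truly stable disease; 5 equal marker lesions; 30 lesions, 15 of them raised; log-normal error of standard deviation s on each diameter and each count, with counts rounded to whole numbers; comparison with an entry value that carries the same error; a rise of at least max(25%, 5) for both counts. The two-measurement rule requires a positive visit and a positive repeat.

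**4. Chance per visit of crossing a threshold ratio R.** Before rounding, P = 1 − Φ(ln R / (σ√2)), where σ is the log-scale error of the quantity compared. At s = 10%:
- Marker area: σ = 10% × √2 / √5 = 6.3%. P = 1 − Φ(0.223/0.089) = 0.6%.
- Total count: σ = 10%, R = 1.25. P = 1 − Φ(0.223/0.141) = 5.7%.
- Raised count: σ = 10%, R = 20/15 = 1.33. P = 1 − Φ(0.288/0.141) = 2.1%.

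The counts drive the result.

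**5. False progression by week 36, simulated, all three criteria.**

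| Error s | One visit | Two measurements, independent errors |
|---|---|---|
| 5% | 0.6% | <0.1% |
| 7.5% | 9.2% | 1.4% |
| 10% | 28% | 7% |
| 12.5% | 48% | 18% |
| 15% | 64% | 31% |

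At 10% error, if all 20 participants were stable, that is 20 × 0.28 = 5.6 against 20 × 0.073 = 1.5 false events.

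**6. Sensitivity at 10% error.**
- Repeat error correlated with the first reading: about 28% against 13% (correlation 0.5) and 28% against 18-19% (correlation 0.8).
- Marker area alone: about 2.8% against 0.3%.
- Five-lesion minimum for raised lesions applied only when they are few, as Appendix D 2.3 words it for participants with 50 or fewer lesions: about 37% against 12%.
- Marker area alone, but with 10% error on the summed area itself: 18.7% against 5.1%.

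The direction is the same in every setting. The size is not stable.

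**The case against.** The strongest reply is that the appendix is silent, not contradictory. It sends the reader to the protocol body for definitions; the section number is wrong, but 12.1.2 is the only place it can mean. On that view its examples only teach percentage arithmetic, and Section 12.1.2.4 governs. This has some force. But the appendix spells out confirmation for PR, CR and edema, so its omission for the measured PD criteria reads as deliberate, and its examples do assign progression at one visit. Section 9.4.2 does not settle the matter.

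Four stronger readings are tempting and should not be drawn:
- **That Section 12.1.2.4 forbids one-reading progression.** It says when feasible, so confirmation is a default. The simulation treats it as absolute and to that extent overstates the contrast.
- **That the second measurement may never be taken.** Section 6.6 read alone suggests this, because it moves participants to survival follow-up after progression. But Section 6.5 and note o schedule a re-evaluation, and note d limits survival-only follow-up to those who start new treatment or stop study treatment for documented progression. The gap is that no text makes the re-evaluation decide PD.
- **That a false PD cancels a response already confirmed.** Section 9.4.1 uses best response within 12 months, so a later false PD leaves a confirmed PR in place. Section 12.1.2.3 also bars PR when PD is present, so the override is not peculiar to the appendix. A one-reading PD could still block a PR that is not yet confirmed; that was not quantified.
- **That 28% against 7% is this trial's error rate.** The documents give no error size, and total and raised counts were drawn independently although one contains the other.

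**Conclusion.** The point holds as an inconsistency in current text, with a missing rule and a missing date in Section 9.4.2. It stands without the simulation: the same readings can give different PFS, duration of response and response calls. The simulation adds that a one-visit rule yields more false progression in stable disease, negligibly at 5% error and substantially at 10% or more, and mainly through lesion counts. The figures are conditional on the assumed error size, on independent repeats and on the assumed lesion numbers.

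Only secondary estimates are affected. The DLT-based primary endpoint is untouched, and Section 9.4.1 leaves a more precise efficacy estimate to a later expansion cohort. The change should be made, but the trial's main conclusion does not depend on it.

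**What to change.** - In Appendix D 2.1 to 2.3 and the PD table in 2.4, state that PD by marker area, lesion count or raised-lesion count follows the Section 12.1.2.4 confirmation: two measurements at least 1 week apart, when feasible.
- Correct the Appendix D reference from Section 12.3 to 12.1.2.
- In Section 9.4.2, name that rule for PFS and duration of response, and state that a confirmed PD is dated at the first of the two readings.
- Note that the re-evaluation in Section 6.5 and calendar note o can supply the second measurement. The 1-week minimum interval need not change.
- Reconcile Section 6.6 with calendar note d on when survival-only follow-up begins. Which of the two is right is for the sponsor to decide.

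The cost is wording; the re-evaluation is already planned. The downside is that PD status is known somewhat later, by up to about 5 weeks where the 4-week visit (plus its 1-week window) is the second measurement.

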#### 12.1.2.5 Stable Disease

Any tumor measurement not meeting the criteria for Complete Response, Partial Response or Progressive Disease.

## **13. STUDY OVERSIGHT AND DATA REPORTING / REGULATORY REQUIREMENTS**

Adverse event lists, guidelines, and instructions for AE reporting can be found in [Section 10](#) (Adverse Events: List and Reporting Requirements).

### **13.1 Study Oversight**

This protocol is monitored at several levels, as described in this section. The Protocol PI is responsible for monitoring the conduct and progress of the clinical trial, including the ongoing review of accrual, patient-specific clinical and laboratory data, and routine and serious AEs; reporting of expedited AEs; and accumulation of reported AEs from other trials testing the same drug. The Protocol PI and statistician have access to the data at all times.

All decisions regarding dose escalation/expansion/de-escalation require sign-off by the Protocol PI. In addition, the Protocol PI will have at least monthly, or more frequently, conference calls with the Study Investigators to review accrual, progress, and adverse events and unanticipated problems.

All Study Investigators at participating sites who register/enroll patients on a given protocol are responsible for timely submission of data via Medidata Rave and timely reporting of AEs for that particular study. This includes timely review of data collected on the electronic CRFs submitted via Medidata Rave.

All studies are also reviewed in accordance with the enrolling institution's data safety monitoring plan.

### **13.2 Data Reporting**

Medidata Rave is a clinical data management system being used for data collection for this trial/study. Access to the trial in Rave is controlled through the CTEP-IAM system and role assignments.

Requirements to access Rave via iMedidata:

- A valid CTEP-IAM account; and
- Assigned a Rave role on the LPO or PO roster at the enrolling site of: Rave CRA, Rave Read Only, Rave CRA (LabAdmin), Rave SLA, or Rave Investigator.

Rave role requirements:

- Rave CRA or Rave CRA (Lab Admin) role must have a minimum of an Associate Plus (AP) registration type;
- Rave Investigator role must be registered as an Non-Physician Investigator (NPIVR) or Investigator (IVR); and

- Rave Read Only role must have at a minimum an Associates (A) registration type.

Refer to <https://ctep.cancer.gov/investigatorResources/default.htm> for registration types and documentation required.

This study has a Delegation of Tasks Log (DTL). Therefore, those requiring write access to Rave must also be assigned the appropriate Rave tasks on the DTL.

Upon initial site registration approval for the study in Regulatory Support System (RSS), all persons with Rave roles assigned on the appropriate roster will be sent a study invitation email from iMedidata. To accept the invitation, site staff must either click on the link in email or log in to iMedidata via the CTSU members' website under *Data Management > Rave Home* and click to *accept* the invitation in the *Tasks* pane located in the upper right-corner of the iMedidata screen. Site staff will not be able to access the study in Rave until all required Medidata and study specific trainings are completed. Trainings will be in the form of electronic learnings (eLearnings) and can be accessed by clicking on the eLearning link in the *Tasks* pane located in the upper right corner of the iMedidata screen. If an eLearning is required for a study and has not yet been taken, the link to the eLearning will appear under the study name in the *Studies* pane located in the center of the iMedidata screen; once the successful completion of the eLearning has been recorded, access to the study in Rave will be granted, and a *Rave EDC* link will replace the eLearning link under the study name.

Site staff that have not previously activated their iMedidata/Rave account at the time of initial site registration approval for the study in RSS will receive a separate invitation from iMedidata to activate their account. Account activation instructions are located on the CTSU website in the Data Management section under the Rave resource materials (Medidata Account Activation and Study Invitation Acceptance). Additional information on iMedidata/Rave is available on the CTSU members' website in the Data Management > Rave section at [www.ctsu.org/RAVE/](http://www.ctsu.org/RAVE/) or by contacting the CTSU Help Desk at [name] or by email at [[contact]](mailto:[contact]).

